3.1 Inclusion Criteria for Patient

Women 18 years of age and older, who are waiting to have a mammogram

Women agree to complete informed consent and registration forms allowing follow-up reminders and access to their EMR record limited to the visit with a dermatologist or primary care physician regarding a concerning skin lesion and the results of the biopsy of the lesion.

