3.0 Procedures Involved

3.1 Study Design

Phase 1: *Delivery of educational SSE program.*

Each of the eight changing rooms of the Lynn Sage Comprehensive Breast of Northwestern Memorial Hospital will be equipped with a poster, brochures (Fig 1 and Fig 2) and cards with information about obtaining an appointment with a dermatologist for concerning skin lesions.

A woman research assistant will obtain consent to participate in the research and review of medical information, collect contact information and if the woman owns an iPhone X, 8+ or 8, and ensure receipt of an informational brochure. Women will be asked if they own an iPhone X, 8+ or 8 to assess the prevalence of these specific phones in the population of interest. These iPhones models are of particular interest to the research team as they offer superior image quality compared to older models. If a woman has this type of phone, she will be asked about her experience using it to take close-up pictures. The woman will be asked her preference for being contacted by email, telephone, or text message. The two arms of the study will be delivered on different weeks. During weeks 1,3,5 and 7 of the study period 400 women will be given brochures and a card with information on scheduling dermatology follow-up prior to check-out (Group 1), (Fig 3). During weeks 2, 4, 6 and 8 of the study period, 400 women will be given brochures to perform SSE at home and proceed to check-out of the mammogram area (Group 2). The women in Group 1 will also receive a reminder about performing a SSE one week after their mammogram visit via phone call,

Effect of SSE education delivered during the mammography experience.

email or text message. One month after the mammogram visit both groups will be called and surveyed to see if they checked their skin and/or made an appointment to see a dermatologist. Three months after the mammogram, both groups will be asked to participate in a complete survey (either via REDCap or telephone), including whether the women followed up in dermatology and if any concerning lesions were biopsied.

Fig 1. SSE Poster

[figure not shown]
[figure not shown]

Fig 2. Cover of SSE

[figure not shown]

Phase 2: Assessment of SEE Implementation

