3.3 Research procedures and activities

Follow-Up

1 week after the mammogram, RA will contact participants in group 1 via their preferred method to remind them to perform SSE and schedule a dermatologist appointment if they find a concerning mole. (see attached telephone script)

1 month after the mammogram, the RA will call participants in group 1 and administer a survey to see if they checked their skin and/or made an appointment with a dermatologist.

Effect of SSE education delivered during the mammography experience.

(see attached telephone script) An anonymous REDCap survey may be used in place of the telephone call, depending on participant's preferred method of contact preference.

The survey questions are as follows:

1. Did you read the brochure?
 Yes No
2. Did you check your skin? (If no, please proceed to question #4)
 Yes No
3. If yes, did you notice any concerning moles?
 Yes No
4. If no, will you consider checking your skin in the future?
 Yes No
5. If you found any concerning moles, did you make an appointment to see a dermatologist?
 Yes No

If no, do you intend to do so in the near future?

6. Did you share the brochure with anyone else?
 Yes No
7. If yes, who did you share it with:
 - a) A relative: son, daughter, father, mother, sister, brother
 - b) A friend : woman, man
 - c) Someone I work with: woman, man

REDCap Survey

3 months after the mammogram, an anonymous REDCap survey will be emailed to each woman enrolled in both groups. If participants do not complete the REDCap survey in 2 weeks, they will be called and surveyed via telephone. The following items with relevance to the research:

1. Do you have a history of sunburn? Yes/No
2. Do you have a history of more than 10 indoor tanning sessions? Yes/No
3. Do you have a personal or family history of melanoma? Yes/No
4. Have you ever performed a skin self-examination prior to your most recent mammogram? Yes/No

Effect of SSE education delivered during the mammography experience.

5. Did you perform a skin self-examination after your most recent mammogram?
Yes/No
If no, then go to item 8.
6. Did you find a concerning mole? Yes/No
7. If you found a concerning mole, did you make an appointment to see a dermatologist? Yes/No
8. If you did not perform a skin self-examination, did you still make a follow-up appointment to see a dermatologist for a skin examination? Yes/No
9. Have you had an appointment with a dermatologist yet? Yes/No

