10. If you found a concerning mole and saw a dermatologist, was the concerning mole biopsied? Yes/No
 - a. If yes, was the biopsy done at Northwestern? Yes/No
 - b. If No, were you told by your dermatologist that the skin biopsy was melanoma? Yes/No
11. If you saw a dermatologist, were any other concerning moles biopsied? Yes/No

EMR review

If a woman responds yes to item 9 indicating that they made an appointment with a dermatologist, then the EMR will be checked to ascertain the findings of the dermatologist. The pathology report of biopsied mole(s) will be reviewed and added to the deidentified database.

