14.0 Data Analysis

14.1. This convenience sample of women undergoing screening mammography will all receive education either as a brochure and a 1-week reminder or as only the brochure. Demographic characteristics of the two groups will be examined using means and standard deviations (age) and counts and percentages for all categorical variables. Primary outcomes of SSE performance, biopsy, and diagnoses will be compared using Chi-square tests of association or Fisher's exact tests where sample sizes were restrictive. Due to the skewed nature of the anxiety scale, a Wilcoxon rank sum test will be used to compare anxiety, the secondary outcome, in the two groups. Descriptive statistics will be performed for the tertiary outcome of dissemination.

15.0 Confidentiality and Data Management:

1. There are no biological specimens. All of the following data is collected in person consent and responses to structured interviews and focus groups.
2. Our systems are guarded against outside entry by Northwestern's own firewall supporting 128-bit encryption. This level of encryption provides the highest level of protection against hackers, computer break-ins, etc. All data is deidentified. Experienced research assistants will be employed and will receive training that includes emphasis upon the importance of confidentiality of information, and all personnel on the project will complete the required NIH training in the protection of human research participants.
3. Data will be retained in separate locked file cabinets and on computers with restricted and password protected access, without links to the master code list. All data based on the research will be reported in aggregate form. No individual respondents will be identified. Electronic data will be maintained in a study specific database on the server of the Department of Dermatology at the Feinberg School of Medicine. Paper-based files will be kept in a locked cabinet in a locked room within the Northwestern University Department of Dermatology research offices. Identifiable data will be kept separate from the case report forms and source documents. Data gathered as a result of this study are available to inspection on request by Food and Drug Administration or other government regulatory agency auditors, and the Northwestern University Institutional Review Board (IRB).

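### EMR consent covers dermatology and primary care visits, but every care-seeking item, biopsy item and chart-review trigger names only a dermatologist, so biopsies done solely in primary care go unrecorded

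*Combined protocol and SAP*

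**What the plan says.** **Permission.** Section 3.1 (Inclusion Criteria for Patient) has women agree to record access "limited to the visit with a dermatologist or primary care physician regarding a concerning skin lesion and the results of the biopsy of the lesion". Primary care is therefore foreseen as a route for a concerning mole.

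**Measurement.** Section 3.3 (Research procedures and activities) does not follow that route.
- One-month item 5: "If you found any concerning moles, did you make an appointment to see a dermatologist".
- Three-month item 7: "If you found a concerning mole, did you make an appointment to see a dermatologist".
- Three-month item 8, for women who did not examine themselves: "did you still make a follow-up appointment to see a dermatologist for a skin examination".
- Three-month item 9 asks whether a dermatology appointment has taken place.
- Three-month item 10: "If you found a concerning mole and saw a dermatologist, was the concerning mole biopsied". Its part b, on a melanoma result, asks what the dermatologist said. Item 11, on other biopsied moles, is also conditional on having seen a dermatologist.
- EMR and pathology review starts from a yes to item 9. Section 3.4 (Measures) likewise ties chart review to follow-up in dermatology.

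**Privacy.** Section 13.2 describes EMR access as covering women with a dermatologist visit for a concerning mole. Primary care is not mentioned.

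**Analysis.** Section 14.0 states: "Primary outcomes of SSE performance, biopsy, and diagnoses will be compared using Chi-square tests". Section 3.4 instead lists biopsy among the quantities to be described, and tests only SSE performance and seeing a dermatologist.

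**The concern.** The consent anticipates a primary care route that no data-collection step can record. Consider a woman who finds a mole, takes it to her primary care physician, has it biopsied there and never sees a dermatologist. She correctly answers no to item 9, items 10 and 11 do not apply to her, and no chart is opened. Her biopsy and its pathology are missing from two of the three outcomes that section 14.0 calls primary.

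If such losses are equally common in both arms, events and power are lost. If they are more common in one arm, the comparison of biopsies and diagnoses is also biased. A difference by arm is conceivable because only Group 1 is handed a dermatology scheduling card before check-out and, at one week, a reminder that mentions booking a dermatologist.

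**Working it through.** **1. Which outcomes are affected**

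| Outcome | Where recorded | Affected? |
|---|---|---|
| SSE performed | three-month item 5 | No, provider-neutral |
| Concerning mole found | three-month item 6 | No, provider-neutral |
| Saw a dermatologist | three-month item 9 | No, dermatology-specific by design |
| Biopsy | items 10 and 11, EMR | Yes, if biopsied only in primary care |
| Diagnosis | item 10b, EMR and pathology report | Yes, same women |

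A woman referred on from primary care who has seen a dermatologist before the three-month survey answers yes to item 9 and is captured.

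**2. Inputs**
- From the documents: 400 women per arm (section 3.1, Study Design) and 20% anticipated attrition (Phase 2 text). Analysed per arm, if attrition is equal: 400 × (1 − 0.20) = 320.
- The documents give no sample-size calculation, expected biopsy rate or primary-care share, so there is no stated figure to reproduce.
- Assumed: true biopsy rates, the share *s* of biopsied women handled only in primary care, and a two-sided 5% level. A woman with items 10 and 11 blank is counted as not biopsied. The plan does not state the coding, but this is the reading that keeps all respondents in the denominator.

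**3. Formulas**
- Recorded rate = true rate × (1 − *s*).
- Pooled two-proportion test with n = 320 per arm, d = p1 − p2 and p̄ the mean of p1 and p2: SE0 = √[2p̄(1 − p̄)/n]; SE1 = √[(p1(1 − p1) + p2(1 − p2))/n].
- Rejection probability = Φ[(d − 1.96·SE0)/SE1] + Φ[(−d − 1.96·SE0)/SE1].

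**4. Equal loss, with a real difference of 10% v 5%**
- No loss: SE0 = 0.02082, SE1 = 0.02073. Φ[(0.05 − 1.96 × 0.02082)/0.02073] = 0.671.
- 20% loss in both arms: recorded rates 8% v 4%, SE0 = 0.01877, SE1 = 0.01871. Φ[(0.04 − 1.96 × 0.01877)/0.01871] = 0.568.
- Power falls from about 67% to about 57%. The second tail is negligible here.

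**5. Unequal loss, with no real difference**

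Shares of 10% (Group 1) and 30% (Group 2); recorded ratio 0.9/0.7 = 1.29:

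| True rate, both arms | Recorded, Group 1 v Group 2 | Biopsies lost, Group 1 v Group 2 | False-positive probability |
|---|---|---|---|
| 2% | 1.8% v 1.4% | 0.6 v 1.9 | 6.9% |
| 5% | 4.5% v 3.5% | 1.6 v 4.8 | 9.9% |
| 10% | 9.0% v 7.0% | 3.2 v 9.6 | 15.4% |

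With shares of 10% in both arms the ratio is 1.00 and the false-positive probability stays at 5%.

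**6. The same shares in counts**

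With 15 true biopsies per arm, the expected recorded numbers are 15 × 0.9 = 13.5 and 15 × 0.7 = 10.5, a gap of three. At 320 per arm, p̄ = 24/640 = 0.0375, SE0 = 0.01502 and z = (3/320)/0.01502 = 0.62, so p is about 0.53.

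**The case against.** **The measurement follows the aims.** Section 1.0 is about follow-up with a dermatologist, and the accuracy measure in section 3.4 compares the woman's judgement with the dermatologist's. This stands for the outcome of seeing a dermatologist, which should remain as it is. It does not stand for biopsy and diagnosis, which section 14.0 defines without reference to provider and for which the consent already names primary care.

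**Biopsy may not be a tested outcome.** Section 3.4 treats it descriptively and tests two outcomes that this gap does not touch. This stands as a limit on the consequences. If section 3.4 governs, the harm is an undercount in a descriptive table and not a distorted test. Section 14.0 nevertheless names biopsy and diagnoses as primary and compares them between arms.

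**The difference by arm is conjecture.** A reader might infer that the loss falls mainly on the brochure-only arm and that the plan will therefore produce a false excess of biopsies in Group 1. The documents do not support that. Section 3.1 (Study Design) puts dermatology appointment cards in all eight changing rooms, and section 10.1 has a concerned control subject directed to her own dermatologist. Both would shrink any difference, and no primary-care share is given for either arm. Even with the assumed 10% and 30%, the expected gap in step 6 is only three events, and Fisher's exact test, which section 14.0 allows, would be more conservative than the figures in step 5.

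**Not every item is affected.** A reader might also take the gap to cover the whole follow-up, or to mean that any mole shown to a primary care physician is lost. Neither is so, as step 1 shows.

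**Conclusion.** The mismatch is real and can be read directly from the text. Primary care visits are within the consent in the inclusion criteria, outside every care-seeking and biopsy item and the chart-review trigger, and absent from the access described in section 13.2. Its reach is narrow: women biopsied only in primary care who have no dermatology visit before the three-month survey. For them the plan captures neither biopsy nor pathology.

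Lost events and power are the consequence that needs no assumption about arms: about ten percentage points of power in the example of 10% v 5% with a 20% loss. Bias between arms is a possibility only; the false-positive range of about 7% to 15% holds only under the assumed 10% and 30% shares. All these sizes are illustrative, because the documents supply no biopsy rates or primary-care shares. This is a worthwhile, inexpensive improvement to the measurement and not a flaw that undermines the trial.

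**What to change.** - Reword the three-month visit items (7 to 9) to ask about any clinician seen about the skin, with a tick-box for provider type: dermatologist, primary care physician, other.
- Ask items 10 and 11 of every woman seen by any clinician about her skin, and make item 10b refer to the treating clinician. That also covers biopsies done outside Northwestern.
- Open the EMR after a yes for either a dermatology or a primary care visit about a concerning lesion, and change section 3.4 to match.
- Reconcile section 13.2 with the inclusion criteria before any primary care record is opened. Until the two agree, the extra reviews cannot simply be treated as covered.
- Keep seeing a dermatologist as its own outcome, derived from the tick-box. Base biopsy and diagnosis on all providers.

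The cost is slightly longer survey wording, one tick-box and a few more chart reviews.

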3.4 Measures

The number of women with risk factors for melanoma, who performed SSE after the screening mammogram, who found a concerning mole, who saw dermatology, who had a concerning lesion biopsied in each group will be analyzed by descriptive statistics. The difference in proportions of women who 1) performed SSE 2) saw a dermatologist in the educational intervention group from the intensive intervention group will be compared using a χ^2 test. If the woman responded “yes” to follow-up in dermatology, a chart review of the electronic medical record will be performed to assess whether any lesions were biopsied and pathology of the concerning lesions. The accuracy of the woman’s selection of a concerning lesion will be assessed by examining the correspondence rate between the woman’s assessment during SSE and the dermatologist. The overall correspondence rate will be calculated with a random intercept-only mixed logistic regression model. The statistical analysis will be performed by [name], MPH.

Online data

REDCap survey (see page 8 above)

Approvals required

Effect of SSE education delivered during the mammography experience.

[name] obtained permission for this research to be conducted in the Lynn Sage Comprehensive Breast Center of Northwestern Medicine/Prentice Women's Hospital

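### The lesion-accuracy measure cannot be verified as same-lesion, because the survey items shown never record where the woman's mole was; it is at best a positive predictive value among women seen

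*Combined protocol and SAP*

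**What the plan says.** Section 3.4 Measures plans to judge the accuracy of the woman's "selection of a concerning lesion will be assessed by examining the correspondence rate between the" woman at SSE and the dermatologist. It adds: "The overall correspondence rate will be calculated with a random intercept-only mixed logistic regression model". It does not say what counts as agreement, what the unit is (woman or lesion), who is in the denominator, or what the random intercept is for.

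The woman's side comes from the three-month REDCap survey in Section 3.3 Research procedures and activities. Item 6 reads "Did you find a concerning mole? Yes/No". Item 10 asks "If you found a concerning mole and saw a dermatologist, was the concerning mole biopsied", and item 11 asks separately "If you saw a dermatologist, were any other concerning moles biopsied". The one-month survey and the survey in Section 3.2 are also yes/no on this point.

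The dermatologist's side comes from the chart. The EMR review paragraph opens "If a woman responds yes to item 9 indicating that they made an appointment with a dermatologist" and goes on to the dermatologist's findings and the pathology of biopsied moles. The inclusion criteria describe a narrower permission: "access to their EMR record limited to the visit with a dermatologist or primary care physician regarding a concerning skin lesion". Section 13.2 is similarly narrow.

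**The concern.** A correspondence rate for a selected lesion needs both parties to be speaking of the same lesion. The plan has a dermatologist's chart on one side and a yes/no answer on the other. If a woman worried about a mole on her arm and the dermatologist biopsied one on her back, nothing in the chart review would reliably show that these differ.

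There is also a question of what the rate measures. It conditions on a woman having selected a lesion and having been seen. Section 1.0 presents the project as building on a training programme in which patients' lesion evaluations were accurate against dermatologists' examinations, so a reader could take the new rate as a comparable accuracy. A predictive value among women who chose to attend says nothing about lesions that women overlooked. The site of the mole is hard to recover once the surveys are closed, so the point is worth settling before data collection.

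**Working it through.** The plan states no expected rate, precision or sample size for correspondence, so there is no figure to reproduce. The check compares what the measure needs with what is collected, then illustrates the size under assumptions.

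**1. Needed against collected.**
- Which mole she meant: not recorded. Item 6 is a single yes/no, and no item shown asks for site, number, description or photograph.
- Whether hers was biopsied: item 10, by self-report.
- Whether others were biopsied: item 11, by self-report.
- Which pathology report is hers: no step described.
- Her mole examined but not biopsied: no item, and no step to find it in the chart.
- Several lesions per woman: if the random intercept is for the woman, the model needs lesion-level records, which item 6 does not supply. The cluster is not named.

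**2. Effect of unmatched scoring (assumed inputs).** Let p be the true same-lesion agreement and q the chance that, when her lesion is not confirmed, the dermatologist flags a different one. If any flagged lesion is scored as agreement, the rate is p + (1 − p)q.
- p = 0.70, q = 0: 0.70, no inflation.
- p = 0.70, q = 0.20: 0.70 + 0.30 × 0.20 = 0.76.
- p = 0.70, q = 0.40: 0.70 + 0.30 × 0.40 = 0.82.
- p = 0.40, q from 0.10 to 0.50: 0.46 to 0.70.

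**3. The direction is not fixed.** Item 10a recognises biopsies outside Northwestern. Suppose a share m of visits leaves no chart and is scored as disagreement, unrelated to true agreement. The rate becomes (1 − m) × [p + (1 − p)q]. With m = 0.20 and p = 0.70:
- q = 0: 0.80 × 0.70 = 0.56.
- q = 0.20: 0.80 × 0.76 = 0.608.
- q = 0.40: 0.80 × 0.82 = 0.656.

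All three lie below 0.70. At q = 0.20 the two effects cancel at m = 1 − 0.70/0.76 = 0.079.

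**4. What a predictive value hides.** From the documents, 800 × (1 − 0.20) = 640 women after attrition. Assume 10% have a lesion that a dermatologist would find concerning (64 with, 576 without) and, for simplicity, that all are examined.
- Sensitivity 0.90, false-positive rate 0.06: 57.6 true and 34.56 false positives; PPV = 57.6/92.16 = 0.625; 6.4 missed.
- Sensitivity 0.45, false-positive rate 0.03: 28.8 true and 17.28 false positives; PPV = 28.8/46.08 = 0.625; 35.2 missed.

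The PPV is the same, while about 6 lesions are missed in one case and 35 in the other.

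**5. Likely denominator (assumed ranges).** 640 × SSE performed (0.3 to 0.7) × mole found (0.05 to 0.20) × seen (0.3 to 0.6):
- Low end: 640 × 0.3 × 0.05 × 0.3 = 2.9.
- High end: 640 × 0.7 × 0.20 × 0.6 = 53.8.

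So there would be about 3 to 54 women. Even at 54, the 95% half-width at a rate of 0.5 is 1.96 × √(0.25/53.8) = 0.13. A few wrong matches would move the estimate.

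**The case against.** The strongest reply is that the survey already makes the distinction. A woman who answers no to item 10 and yes to item 11 is exactly the case in which her mole was left alone and another was biopsied. That stands in part. It covers biopsies only, depends on her report, does not say which pathology report is hers, and leaves out moles examined but not biopsied.

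A reader might infer that the plan counts the wrong lesion as agreement and so overstates accuracy. The documents do not support that. No scoring rule is written, so a wrong-lesion match is possible rather than prescribed, and step 3 shows that the error can run either way.

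A reader might also infer that women who found nothing contribute no data, so that missed lesions can never be seen. That is too absolute as well. Any yes to item 9 triggers chart review, and item 8 covers appointments made without SSE, so some charts of women who found no mole may be reviewed. But those women are self-selected, and the narrower access wording in the inclusion criteria and Section 13.2 may exclude them. They do not give a representative sensitivity.

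Two further replies stand. Section 3.4 speaks of accuracy of selection, which is already conditional on a lesion having been chosen; it does not claim overall accuracy of SSE. And correspondence appears neither in the aims in Section 1.0 nor among the primary, secondary and tertiary outcomes in Section 14.0. The telephone script, the registration form and any chart-abstraction form are not in the documents, so a site question there cannot be ruled out.

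**Conclusion.** The point holds in a limited form. On the items shown, same-lesion agreement cannot be verified, and the rate is at best a positive predictive value among self-selected women who found a mole and were examined. The size and direction of any bias cannot be derived from the documents. Under the assumptions in the working, a true 70% could appear anywhere from 56% to 82%, with no inflation at all if dermatologists never flag a different lesion. The denominator range of about 3 to 54 women also rests on assumed rates.

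Priority is low: neither the comparison of the two groups nor any listed outcome depends on this measure. It is still worth acting on, because the missing item is cheap now and hard to reconstruct later.

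**What to change.** - **Survey.** Add a sub-item to item 6 asking where on the body each concerning mole was, from a short region list, allowing more than one mole. Use it with item 10 to find the lesion in the chart or pathology report.
- **Section 3.4.** State which chart finding counts as agreement, the unit of analysis, the cluster for the random intercept and the denominator. Score agreement only for a lesion at the reported site.
- **Unmatched charts.** Report charts without a recorded site, and visits outside Northwestern, as a separate count with best-case and worst-case bounds. Scoring them as disagreement would pull the rate down.
- **Label.** Call the measure a positive predictive value of the woman's concern among women examined by a dermatologist, and give the number who found a mole but were not examined beside it.
- **Linkage.** Sections 3.1 Study Design and 3.3 call the three-month survey anonymous, yet its answers trigger the EMR review and non-completers are telephoned. Reconcile this by linking survey and chart through the study number already described in Section 15.0, and align the item 9 trigger with the EMR access wording.

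The cost is one extra survey item and some wording, with no added examination. Some charts will remain unmatched, and the gap between the bounds equals their share. Region-level matching is still imperfect, since two moles on the back would match each other.

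### The random-intercept model for the correspondence rate has no stated unit, lesion linkage or reported estimate; on survey data alone it adds nothing to a proportion, and its back-transformed intercept is generally not the overall rate

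*Combined protocol and SAP*

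**What the plan says.** Section 3.4 (Measures) describes the accuracy of a woman's choice of lesion as "examining the correspondence rate between the woman’s assessment during SSE and the dermatologist", and then names the method: "The overall correspondence rate will be calculated with a random intercept-only mixed logistic regression model". It does not say whether the random intercept belongs to the woman or the dermatologist, what counts as agreement, or how a rate is taken from the fitted model. Section 14.0 (Data Analysis) does not mention this analysis.

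The woman's side of the comparison comes from survey items in section 3.3 (Research procedures and activities):

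- One-month survey, item 3: "3. If yes, did you notice any concerning moles".
- Three-month survey, item 6: "Did you find a concerning mole? Yes/No".
- Three-month survey, item 10: "If you found a concerning mole and saw a dermatologist, was the concerning mole biopsied? Yes/No".
- Three-month survey, item 11: "If you saw a dermatologist, were any other concerning moles biopsied".

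The baseline survey in section 3.2 has a similar yes/no item. None of these items asks for a number of moles, a body site or a lesion identifier.

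The dermatologist's side comes from the EMR review in section 3.3, which covers the dermatologist's findings and the pathology of one or more biopsied moles. Neither section describes matching a charted lesion to the one the woman picked out.

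**The concern.** A random-intercept model separates variation between clusters from the mean. If the cluster is the woman, that requires more than one binary result from at least some women. The survey items supply one answer per woman per survey. Asking again at another survey repeats a woman-level answer and does not create lesion-level data.

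A second issue arises even when several lesions per woman are available. The fixed intercept of a logistic mixed model, back-transformed, is the rate for a cluster whose random effect is zero. The plan promises an overall rate, which is the average over clusters. The two differ unless the variance is zero or the rate is one half.

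This is the study's only stated measure of how well women pick out concerning moles. As written, two analysts with the same data could report different rates without departing from the plan.

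**Working it through.** The documents give no correspondence rate, variance or precision target, so there is no stated figure to reproduce. All counts, rates and SDs below are assumptions chosen to show how the model behaves.

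**Model.** For a cluster with random effect σZ, where Z is standard normal, the probability of agreement is expit(b0 + σZ). The overall (marginal) rate is p = E[expit(b0 + σZ)], computed by 120-point Gauss-Hermite quadrature. The back-transformed intercept is expit(b0).

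**Step 1: one record per woman, woman-level intercept.** Suppose 28 of 40 women agree with the dermatologist. The likelihood depends on b0 and σ only through p, so for each σ there is a b0 that gives p = 28/40 = 0.70. The maximised log-likelihood is

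28·ln(0.70) + 12·ln(0.30) = −9.9869 − 14.4477 = −24.4346.

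| SD (σ) | b0 | Log-likelihood | expit(b0) | Marginal rate |
|---|---|---|---|---|
| 0 | 0.847 | −24.4346 | 0.700 | 0.70 |
| 1 | 1.018 | −24.4346 | 0.735 | 0.70 |
| 2 | 1.384 | −24.4346 | 0.800 | 0.70 |
| 3 | 1.823 | −24.4346 | 0.861 | 0.70 |

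The likelihood is flat in σ, so σ is not identified. The marginal rate is identified and equals the raw proportion, 0.70, with an exact 95% CI of 0.53 to 0.83.

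**Step 2: expit(b0) over a range of assumed true rates.**

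| True rate | SD 0 | SD 1 | SD 2 | SD 3 |
|---|---|---|---|---|
| 0.30 | 0.300 | 0.265 | 0.200 | 0.139 |
| 0.50 | 0.500 | 0.500 | 0.500 | 0.500 |
| 0.60 | 0.600 | 0.620 | 0.661 | 0.707 |
| 0.70 | 0.700 | 0.735 | 0.800 | 0.861 |
| 0.80 | 0.800 | 0.839 | 0.903 | 0.949 |
| 0.90 | 0.900 | 0.929 | 0.968 | 0.989 |

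The 0.30 row follows by symmetry from the 0.70 row (for example 1 − 0.735 = 0.265). The shift is away from 0.5 in both directions.

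**Step 3: several linked lesions per woman.** Suppose 40 women have two lesions each, and 7, 10 and 23 of them have 0, 1 and 2 agreements. The observed rate is (10 + 2·23)/80 = 56/80 = 0.70. The profile log-likelihood is −41.94, −39.96, −38.81 and −39.11 at σ = 0, 1, 2 and 3, so σ is now estimable; its maximum-likelihood estimate is about 2.17. At that fit b0 = 1.454 and expit(b0) = 0.81, while the marginal rate is 0.70. Linked lesions therefore solve the identifiability problem but leave the choice between a conditional and a marginal rate open.

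**The case against.** A reader might infer that the variance is simply not identifiable and that the plan will report an inflated rate. The documents do not support either statement in that form, for four reasons.

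- **Data structure.** The comparison is not drawn from the surveys alone. The EMR review could give several lesions per woman. If the chart shows which lesions she raised, the variance is estimable, as in step 3. What stands against this is that the plan describes no such linkage, and item 11 does not say that the other biopsied moles were ones she had selected.
- **Clustering unit.** The plan does not say the intercept is by woman. A dermatologist-level intercept could be identified from one record per woman if several women saw the same dermatologist. The plan does not state that either, and a back-transformed intercept would still be conditional.
- **Reported estimate.** The plan says the rate is calculated with the model, not that it is the back-transformed intercept. A marginal rate from the same model is valid, and with one record per woman it equals the raw proportion. This objection stands: the distortion depends on a choice the plan leaves open.
- **Direction.** Nothing in the documents indicates that the rate will exceed 50%. Below that, the intercept understates it.

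The reach is also limited. This is a descriptive figure with no between-arm test attached, and it is not among the outcomes listed in section 14.0.

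**Conclusion.** The point holds as conditional under-specification. Section 3.4 fixes a model but leaves out the clustering unit, the lesion linkage and the estimate to be reported. If the data are one result per woman and the intercept is by woman, the variance is not identifiable and the model gives nothing beyond the observed proportion. With one lesion or several, a back-transformed intercept would miss the overall rate unless the SD is 0 or the rate is 0.5.

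If the intercept were reported, the error at an assumed true rate of 0.70 would be 3.5 percentage points at SD 1 (0.735 − 0.700), 10 at SD 2 and about 16 at SD 3. It would be equally large but downward at 0.30, and zero at 0.50. No documented value shows which of these applies. The chi-square and Fisher comparisons between arms are untouched, so this should be corrected but does not threaten the main analysis.

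**What to change.** In section 3.4, replace the sentence naming the model with:

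> The overall correspondence rate is the observed proportion of women (or of lesions, if the chart review links more than one lesion to a woman's own selection) for whom her assessment agrees with the dermatologist's, with an exact 95% CI when there is one record per woman and a CI from cluster-robust standard errors by woman when there are several. If a mixed model is kept, the marginal rate integrated over the random effect is reported, not the back-transformed intercept.

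The same passage should say what counts as agreement, because no analysis method supplies that definition. The cost is a short change of wording. It needs no new data, and the code is simpler than for the mixed model. The replacement estimates the overall rate under either data structure.
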